6.7.1 Collection of pharmacodynamic markers

Blood samples (10 mL) for ADP-induced platelet aggregation will be taken at the times presented in the study plan [Table 2](#).

For blood volume see Section [7.1](#).

6.8 Pharmacogenetics – Not applicable

6.9 Health economics – Not applicable

7. BIOLOGICAL SAMPLING PROCEDURES

7.1 Volume of blood

The total volume of blood that will be drawn from each subject in this study is as follows:

Table 3 Volume of blood to be drawn from each subject

Assessment		Sample volume (mL)	No. of samples	Total volume (mL)
Safety	Clinical chemistry	4	4	16
	Haematology	2	4	8
PK		3	12	36
PD		10	12	120
Total				180

7.2 Handling, storage and destruction of biological samples

The long-term stability of the analyte(s) should be described in validation report of bioassay established by the AstraZeneca R&D Drug Metabolism and Pharmacokinetics (DMPK) department. Results from analyses of samples stored longer than the time period for which stability has been certain should not be reported unless complementary analyte(s) stability data is acquired and amended to the relevant validation report. The time period for which stability has been demonstrated should be documented by the AstraZeneca R&D DMPK department prior to the first patient gives informed consent to take part in the study.

7.2.1 Pharmacokinetic samples

Samples will usually be taken by direct venipuncture. A 3mL sample of blood will be drawn into a collection tube containing lithium heparin and the heparin and blood will be mixed carefully. The sample will be placed on ice until centrifugation, which will begin within 30 minutes of the sample being obtained. The blood sample will be centrifuged for 10 minutes at a relative centrifugal force of 1500 g. The resultant plasma will be transferred to a plain polypropylene tube (screw top) and immediately frozen upright at or below -20°C until transfer for analysis. Here, all blood sampling equipments will be provided from the central laboratory. The frozen samples must be stored at -20°C or lower, before, during and after transport. A log recording daily temperature readings of the freezer used to store samples at the investigational centre must be maintained.

Individual venepunctures for blood collection at each time point are highly recommended to avoid contamination of saline and heparin by using indwelling venous cannula. However, according to the discretion of investigator, indwelling venous cannula may be used. In that case, saline (heparin must not be used) should be used to keep the cannula patent. On each sampling occasion, the first blood in the cannula should be discarded using plain syringe. And, it should be flushed with saline after each sample is obtained. In case cannula is occluded, venepuncture should be done for further sample collection.

The frozen samples must be packed securely to avoid breakage and contain any leaks during transit and should be packed with a sufficient quantity of dry ice to ensure they remain frozen for at least 72 hours to allow for delays in shipment. All applicable shipping regulations will be followed.

Samples for PK determination of AZD6140 and the metabolite AR-C124910XX will be analysed only for the patients receiving AZD6140 by a certified laboratory using validated bioanalytical methods.

7.2.2 Pharmacodynamics samples

Samples for the measurement of platelet aggregation will be drawn through the same cannula used for PK sampling. At time points where PK and PD (aggregometry) samples coincide, samples may be taken in any order since equal priority is given; however, in the event of a sampling difficulty the PD sample should be prioritised.

At each time point specified in the study plan in [Table 2](#), one 10 mL venous blood sample will be collected into a plain syringe. From this 9.0 mL will be transferred into a tube containing 1 mL trisodium citrate dihydrate.

Pre-dose samples should be obtained shortly (within 30 minutes) before dosing with the investigational product. The pre-dose sample at Visit 2 is a critical baseline sample and enough time should be allowed for a repeat sample and analysis should the first aggregometry analysis fail eg, the sample clots, prior to the first dose of investigational product. The date and time of each sample collection will be recorded in the appropriate section of the eCRF.

The samples will be prepared to produce platelet rich plasma (PRP) that will then be assessed using optical aggregometry. Full details of the methodology are given in [Appendix D](#).

Preparation of PRP will start within 15 minutes of blood samples being obtained so that aggregation studies can start one hour (± 10 minutes) after blood sampling to ensure consistency in methodology. Appropriately trained laboratory personnel at each centre will perform all analyses.

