5.5.2 Doses and treatment regimens

At Visit 2 (randomisation) eligible patients will be randomly assigned to one of three treatment arms, AZD6140 45mg, 90mg twice daily or clopidogrel 75mg once daily, taken orally.

Randomisation and treatment pack assignment will be managed via the IWRS and the first dose of study medication should be taken directly after randomisation at Visit 2. Subsequent maintenance doses should be taken morning and evening, at approximately 12-hourly intervals, for the remainder of the treatment period.

Study medication should be swallowed whole with water. Study medication should not be altered (eg, crushed, put in another vehicle) and should not be given by nasogastric tube or other routes.

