11.5 Calculation or derivation of pharmacodynamic variable(s)

Maximum and final extent IPA from pre-dose baseline at Visit 2 will be calculated at all subsequent timepoints using the following formula for ADP-induced platelet aggregation:

$$\text{Percentage Inhibition} = 100\% \times (PAs - PA) / (PAs)$$

PA is the mean response at the given post dose time point and PAs is the mean response at pre dose baseline. Percentage inhibition will be restricted to the closed interval [0,100]; any data falling outside this range will be truncated to the appropriate limit.

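### For the Visit 2 baseline platelet sample, the 30-minute pre-dose window and the repeat-before-first-dose safeguard cannot both be met, because aggregometry starts 50 to 70 minutes after the draw

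*Protocol*

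**What the plan says.** Protocol section 7.2.2 sets three timing rules for the platelet aggregation samples.

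- Window, for all pre-dose samples: "Pre-dose samples should be obtained shortly (within 30 minutes) before dosing with the investigational product".
- Safeguard, for the Visit 2 baseline only: "enough time should be allowed for a repeat sample and analysis should the first aggregometry analysis fail". The sentence goes on to require that this be possible before the first dose, gives clotting as an example of failure, and calls the sample critical.
- Assay lag: the plasma is to be prepared no later than 15 minutes after the draw, and the purpose given is a fixed delay before reading: "so that aggregation studies can start one hour (± 10 minutes) after blood sampling".

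Section 11.5 shows why this sample matters: "Maximum and final extent IPA from pre-dose baseline at Visit 2 will be calculated at all subsequent timepoints using the following formula". The baseline response is the denominator of that formula, and no substitute is named.

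Section 5.5.2 adds that "the first dose of study medication should be taken directly after randomisation at Visit 2". The Visit 2 description in section 3.1 places the pharmacodynamic assessment before study medication, but does not say whether the result must be known before randomisation or dosing.

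**The concern.** The safeguard exists so that no patient is dosed without a usable baseline. It requires the first sample to have been analysed, and if necessary a second one drawn and analysed, before dosing. The assay lag alone is longer than the window in which the sample must be drawn, so a site cannot follow all three sentences.

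At stake is the denominator of the primary variable. With approximately 18 centres each running their own aggregometry, some may keep the window and lose the safeguard, while others keep the safeguard and record a deviation from the window. The critical baseline sample would then be handled differently from site to site with no stated rule.

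**Working it through.** **Inputs.** Draw window: 0 to 30 minutes before dosing (7.2.2). Draw to start of aggregometry: 60 ± 10, so 50 to 70 minutes (7.2.2). Start of platelet-rich plasma (PRP) preparation: within 15 minutes of the draw (7.2.2). Precision: 34 Japanese patients per group, SD 25%, two-sided 95% interval, half-width about 12% (12.3).

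**Step 1: draw inside the window.** For a draw *d* minutes before dosing, aggregometry starts at −*d* + (50 to 70) minutes relative to the dose.

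| Draw before dose | Aggregometry starts after dose |
|---|---|
| 30 min | 20 to 40 min |
| 15 min | 35 to 55 min |
| 0 min | 50 to 70 min |

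No draw inside the window has even begun to be read when the dose is given.

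**Step 2: draw that satisfies the safeguard.** For the first reading to start before dosing, the first draw must be at least 50 minutes before it, outside the window. For an immediate repeat also to reach aggregometry before dosing, the first draw must be 50 + 50 = 100 to 70 + 70 = 140 minutes before it, plus redraw and assay time. If only the repeat *draw* has to precede the dose, the first draw is still at least 50 to 70 minutes before dosing, although the repeat draw can fall inside the window.

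**Step 3: failure seen before aggregometry.** If the first draw is 30 minutes before dosing and a clot is noticed when preparation starts, at the latest 15 minutes after the draw, then 30 − 15 = 15 minutes remain for a redraw inside the window. That redraw is a true pre-dose sample even though it is read after dosing.

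**Step 4: what an unrecovered failure costs one patient.** Table 2 lists 5 later platelet samples at Visit 2 (1, 2, 4, 8 and 12 hours) and 6 at Visit 5 (pre-dose, 2, 4, 8, 12 and 24 hours). Under section 11.5, none of these 11 yields an IPA value without a baseline.

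**Step 5: effect on precision.** Half-width = 1.96 × 25 × √(2/n). With n = 34 this gives 11.9, which reproduces the protocol's figure of about 12%. The protocol gives no baseline failure rate, so the rates below are assumptions. They treat every failure as unrecoverable.

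| Assumed loss | n per group | Half-width |
|---|---|---|
| 0% | 34 | 11.9 |
| 3% | 33.0 | 12.1 |
| 5% | 32.3 | 12.2 |
| 10% | 30.6 | 12.5 |

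**The case against.** The best defence is that the specific sentence qualifies the general one. The window covers all pre-dose samples and is worded as a recommendation. The next sentence singles out Visit 2, and a site could take it as an instruction to draw early and delay dosing until the baseline is read. The repeat is then feasible, and the only cost is a successful first baseline older than 30 minutes, which does no harm because no study drug has been given. This reading is fair, so a reader should not infer that the repeat can never happen. But the text does not state it, and a site that adopts it breaches the window as written.

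Three further inferences are tempting, and the documents do not support them.

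- *Every failed baseline loses all IPA values.* The formula needs a pre-dose draw, not a pre-dose result, and a clot seen at handling or PRP preparation can be redrawn. The loss arises only if dosing goes ahead inside the window and the failure first shows at aggregometry.
- *Section 5.5.2 means the failure is found after randomisation and dosing.* That section fixes the gap between randomisation and dose. It does not place randomisation before the baseline reading.
- *The patient leaves the pharmacodynamic analysis set and is not replaced.* Section 12.1.1 requires post-dose measurements and does not name a baseline, and the no-replacement rule in section 5.9 concerns withdrawn subjects. The patient may stay in the set while contributing no IPA value.

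Appendix D and the aggregometry manual (section 9.2) are not shown and may set the sequence. Even so, the protocol's own sentences would still conflict.

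**Conclusion.** The conflict within section 7.2.2 is established by arithmetic on the protocol's own figures: a 30-minute window against a 50- to 70-minute assay lag. No section of the protocol shown resolves it. The consequence is conditional. A site that keeps to the window and meets a failure visible only at aggregometry has a dosed patient with no IPA at any of the 11 later times. A site that draws early has a valid baseline that breaches the stated window.

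The effect on precision is probably small: 11.9 rising to between 12.1 and 12.5 at assumed losses of 3% to 10%, in a study whose size does not rest on a formal test. The case for changing the text is that the safeguard for the primary variable's denominator cannot be followed as written. It is not a case about power.

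**What to change.** Reconcile the sentences in section 7.2.2. Exempt the Visit 2 baseline platelet sample from the 30-minute window. State that it is drawn at that visit and successfully read, with any repeat, before the interactive web randomisation call. The first dose can then still follow directly after randomisation, as section 5.5.2 asks, and a failed baseline comes to light before the patient is randomised. Keep the 30-minute window for the pharmacokinetic pre-dose sample and for Visit 5.

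The change is to wording and adds no routine sample. Its cost is time at Visit 2: about 1 hour more for a first reading, and up to about 2.5 hours when a repeat is needed (up to 140 minutes to the second reading, plus redraw and assay time), ahead of 12 hours of sampling.

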7.3 Labelling and shipment of biohazard samples

The Principal Investigator ensures that samples are labelled and shipped in accordance with the Laboratory Manual and the Biological Substance, Category B Regulations (materials

containing or suspected to contain infectious substances that do not meet Category A criteria), see Appendix C ‘IATA 6.2 Guidance Document’.

Any samples identified as Infectious Category A materials are not shipped and no further samples will be taken from the subject unless agreed with AstraZeneca and appropriate labelling, shipment and containment provisions are approved.

7.4 Chain of custody of biological samples

A full chain of custody is maintained for all samples throughout their lifecycle.

The Principal Investigator keeps full traceability of collected biological samples from the subjects while in storage at the centre until shipment or disposal (where appropriate) and keeps documentation of receipt of arrival.

The sample receiver keeps full traceability of the samples while in storage and during use until used or disposed of or until further shipment and keeps documentation of receipt of arrival.

AstraZeneca keeps oversight of the entire life cycle through internal procedures, monitoring of study sites and auditing of external laboratory providers.

Samples retained for further use are registered in the AstraZeneca biobank system during the entire life cycle.

7.5 Withdrawal of informed consent for donated biological samples

If a subject withdraws consent to the use of donated biological samples, the samples will be disposed of/destroyed, and the action documented. If samples are already analysed, AstraZeneca is not obliged to destroy the results of this research.

As collection of the biological samples is an integral part of the study, then the subject is withdrawn from further study participation.

The Principal Investigator:

- Ensures subjects’ withdrawal of informed consent to the use of donated samples is notified immediately to AstraZeneca
- Ensures that biological samples from that subject, if stored at the study site, are immediately identified, disposed of /destroyed, and the action documented
- Ensures the laboratory(ies) holding the samples is/are informed about the withdrawn consent immediately and that samples are disposed/destroyed, the action documented and the signed document returned to the study site
- Ensures that the subject and AstraZeneca are informed about the sample disposal.

AstraZeneca ensures the central laboratory(ies) holding the samples is/are informed about the withdrawn consent immediately and that samples are disposed of/destroyed and the action documented and returned to the study site.

8. ETHICAL AND REGULATORY REQUIREMENTS

8.1 Ethical conduct of the study

The study will be performed in accordance with ethical principles that have their origin in the Declaration of Helsinki and are consistent with International Conference on Harmonisation (ICH) /Good Clinical Practice (GCP), applicable regulatory requirements and the AstraZeneca policy on Bioethics and Human Biological Samples.

For Japan, replace the above paragraph with the paragraph below

The study will be performed in accordance with ethical principles that have their origin in the Declaration of Helsinki and are consistent with ICH/GCP, applicable regulatory requirements, The applicable regulatory requirements in Japan are ‘GCP for Trials on Drugs (MHLW Ordinance No. 28, 27 March 1997, partially revised by MHLW Ordinance and their related notifications and the AstraZeneca policy on Bioethics and Human Biological Samples.

8.2 Subject data protection

The Informed Consent Form will incorporate (or, in some cases, be accompanied by a separate document incorporating) wording that complies with relevant data protection and privacy legislation.

For Japan, replace the above paragraph with the paragraph below

The Master Informed Consent Form will explain that:

- Study data will be stored in a computer database, maintaining confidentiality in accordance with national data legislation.
- Subject data will be maintaining confidentiality in accordance with national data legislation.
- For data verification purposes, authorised representatives of AstraZeneca, a regulatory authority, an Ethics Committee may require direct access to parts of the hospital or practice records relevant to the study, including subjects' medical history.
- All data computer processed by AstraZeneca will be identified by study code and enrolment code (E-code).

8.3 Ethics and regulatory review

An Ethics Committee should approve the final study protocol, including the final version of the Informed Consent Form and any other written information and/or materials to be provided to the subjects. The investigator will ensure the distribution of these documents to the applicable Ethics Committee, and to the study site staff.

The opinion of the Ethics Committee should be given in writing. The investigator should submit the written approval to AstraZeneca before enrolment of any subject into the study.

The Ethics Committee should approve all advertising used to recruit subjects for the study.

AstraZeneca should approve any modifications to the Informed Consent Form that are needed to meet local requirements.

If required by local regulations, the protocol should be re-approved by the Ethics Committee annually.

Before enrolment of any subject into the study, the final study protocol, including the final version of the Informed Consent Form, is approved by the national regulatory authority or a notification to the national regulatory authority is done, according to local regulations.

AstraZeneca will handle the distribution of any of these documents to the national regulatory authorities.

AstraZeneca will provide Regulatory Authorities, Ethics Committees and Principal Investigators with safety updates/reports according to local requirements, including SUSARs (Suspected Unexpected Serious Adverse Reactions), where relevant.

For Japan, replace this section with below

An Ethics Committee should approve the final study protocol, including the final version of the Informed Consent Form and any other written information and/or materials to be provided to the subjects. The investigator The Head of the study site will ensure the distribution of these documents to the applicable Ethics Committee, and to the study site staff.

The opinion of the Ethics Committee should be given in writing. The investigator should submit the written approval to AstraZeneca before enrolment of any subject into the study. The head of the study site should submit a notification of direction/determination as well as a copy of the IRB written approval to AstraZeneca before enrolment of any subject should into the study.

The Ethics Committee should approve all advertising used to recruit subjects for the study.

AstraZeneca should approve any modifications to the Informed Consent Form that are needed to meet local requirements.

If required by local regulations, the protocol should be re-approved by the Ethics Committee annually.

The protocol should be re-approved by the IRB annually. The Principal Investigator should submit progress reports to the IRB via the head of the study site at the time of the protocol re-approval.

Before enrolment of any subject into the study, the final study protocol, including the final version of the Informed Consent Form, is approved by the national regulatory authority or a notification to the national regulatory authority is done, according to local regulations.

AstraZeneca will handle the distribution of any of these documents to the national regulatory authorities.

AstraZeneca will provide Regulatory Authorities, Ethics Committees and Principal Investigators with safety updates/reports according to local requirements, including SUSARs (Suspected Unexpected Serious Adverse Reactions), where relevant.

8.4 Informed consent

The Principal Investigator(s) at each centre will:

- Ensure each subject is given full and adequate oral and written information about the nature, purpose, possible risk and benefit of the study
- Ensure each subject is notified that they are free to discontinue from the study at any time
- Ensure that each subject is given the opportunity to ask questions and allowed time to consider the information provided
- Ensure each subject provides signed and dated informed consent before conducting any procedure specifically for the study
- Ensure the original, signed Informed Consent Form(s) is/are stored in the Investigator's Study File
- Ensure a copy of the signed Informed Consent Form is given to the subject
- Ensure that any incentives for subjects who participate in the study as well as any provisions for subjects harmed as a consequence of study participation are described in the informed consent form that is approved by an Ethics Committee.

For Japan, add the below paragraph

If any new information on the study medication becomes available which may influence the decision of the subject to continue the study, the investigator(s) should inform the subject of such information immediately, record this in a written form, and confirm with the subject if he or she wishes to continue the participation in the study. In addition, if the investigator(s) deem it necessary to revise the Informed Consent Form, they should revise it immediately (Refer to Section 9.5). The investigator(s) should re-explain the subjects using updated Informed Consent Form even if although the subjects have already been informed of the new information verbally. Written informed consent to continue participation in the study should be provided separately.

8.5 Changes to the protocol and informed consent form

Study procedures will not be changed without the mutual agreement of the Principal Investigator and AstraZeneca.

If there are any substantial changes to the study protocol, then these changes will be documented in a study protocol amendment and where required in a new version of the study protocol (Revised Clinical Study Protocol).

The amendment is to be approved by the relevant Ethics Committee and if applicable, also the national regulatory authority approval, before implementation. Local requirements are to be followed for revised protocols.

AstraZeneca will distribute any subsequent amendments and new versions of the protocol to each Principal Investigator(s). For distribution to Ethics Committee see Section 8.3.

If a protocol amendment requires a change to a centre's Informed Consent Form, AstraZeneca and the centre's Ethics Committee are to approve the revised Informed Consent Form before the revised form is used.

If local regulations require, any administrative change will be communicated to or approved by each Ethics Committee.

For Japan, replace this section with below

Study procedures will not be changed without the mutual agreement of the Principal Investigator and AstraZeneca. If it is necessary for the study protocol to be amended, the amendment should be submitted to the Head of the Study Site and be approved by its IRB. If applicable, AstraZeneca should submit a notification to the regulatory authority before it is implemented. If a protocol amendment requires a change to a particular centre's Informed Consent Form, then AstraZeneca and the centre's IRB should be notified. Approval of the revised Informed Consent Form by AstraZeneca and by the IRB is required before the revised form is used. If an administrative change is required, such a change should be notified to or approved by each IRB according to local requirements

